Title: Transcranial Infrared Laser Stimulation (TILS) of Prefrontal Cognition in Post-traumatic Stress Disorder (PTSD)

NCT number: NCT03209882

Date: 05/15/2021

Study Protocol

Veterans with PTSD are recruited from local community. Potentially qualified veterans will first undergo a diagnostic clinical interview (visit 1). The PTSD symptom scores and other medical information collected in this visit will be reviewed immediately to determine whether eligibility criteria are met. Eligible individuals will be guided to go through an IRB-approved informed consent form that describes the study and the terms of potential participation in the study. If a person chooses to participate, s/he will be scheduled for an fNIRS screening (visit 2). This screening will confirm whether the veteran shows hypoactivations in the prefrontal cortex in the memory retrieval phase – a precondition for study inclusion.

Table 1. Experimental protocol

Aim	Visit	Task
Evaluations & screening	1	Clinical evaluation and consenting
	2	fNIRS scan
Aim 1	3–4	Pre-treatment fNIRS scan Sham or TILS; bbNIRS measurement Post-treatment fNIRS scan
Aim 2	5–9	Pre-treatment fNIRS scan TILS; bbNIRS measurement Post-treatment fNIRS scan

Veterans who pass the initial evaluations and screening will be instructed to receive once weekly TILS treatment at the same light power for seven weeks (visits 3 – 9). In fact, we will administer a sham treatment and a TILS treatment in a randomized sequence during the first two weeks (visits 3 and 4) to determine any acute neurophysiological effects of TILS compared with those induced by sham. Specifically, these effects include: 1) the prefrontal metabolic/CCO changes measured by bbNIRS during the treatment; and 2) the incremental changes of prefrontal activations and scores from three neutral memory tasks, which will be measured by fNIRS before and after the treatment (i.e., post-treatment measures minus pre-treatment measures). Then, statistical analyses will be conducted to determine the acute neurophysiological effects of TILS compared with sham.

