After the first two sessions, we will administer another five TILS treatments to the veterans (visits 5 – 9) with fNIRS and bbNIRS measurements taken in each visit. Thus, each veteran will receive a total of six TILS treatments. An iterative statistical analysis procedure will be implemented to determine the least number of TILS sessions that can stably up-regulate prefrontal activity, which will be considered as an optimal TILS dosage.

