### Statistical Analysis Plan

TILS/sham-induced changes in HbO2, Hb and CCO concentrations from the initial baseline will be calculated using the UCLn algorithm. We will focus on oxidized CCO concentration because it is directly related to the oxygen metabolism at the cellular level. The mean CCO changes during the treatment period will be analyzed with repeated measures ANOVA (analysis of variance), by using treatment type (TILS, sham) as a within-subject variable and sex (male, female) as an independent variable.

An iterative statistical analysis will be implemented to determine whether the  $i$ th TILS treatment ( $i \leq 6$ ) is sufficient to stably up-regulate the veteran's prefrontal activations and functioning, by interrogating the veterans' incremental changes (post-treatment minus pre-treatment) in the prefrontal activations and behavioral scores in the three memory tasks. Specifically, at the  $i$ th iteration, we will include all the data from the  $i$ th to the 6th treatments. Repeated measures ANOVA will be performed on the included data, in which the treatment number ( $i$  to 6) is a within-subject variable and sex is an independent variable. If no significant main effect of treatment number ( $p < 0.05$ , effect size  $> 0.8$ ) is found at the  $i$ th iteration in either the prefrontal hemodynamic activations or the memory task scores, it means the  $i$ th TILS treatment is sufficient to stabilize the veterans' prefrontal activity and the rest treatments are not necessary. Thus, the  $i$ th TILS treatment will be determined as the optimal dosage for treating the veterans with PTSD.

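### The Aim 2 dosage rule tests only whether TILS sessions differ from each other, so it cannot show the up-regulation it is meant to establish

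*SAP*

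**What the plan says.** The protocol's Aim 2 is to "determine the least number of TILS sessions that can stably up-regulate prefrontal activity, which will be considered as an optimal TILS dosage". The SAP (Statistical Analysis Plan, second paragraph) asks the matching question: whether the ith session "is sufficient to stably up-regulate the veteran's prefrontal activations and functioning". The data are the post-minus-pre changes in activation and behavioural score in three memory tasks. At step i, sessions i to 6 enter a repeated measures ANOVA with treatment number within subject and sex between subjects. If treatment number has no significant main effect (p < 0.05, effect size > 0.8, metric not named), the SAP concludes that the ith "TILS treatment is sufficient to stabilize the veterans' prefrontal activity and the rest treatments are not necessary", and so that the ith "TILS treatment will be determined as the optimal dosage for treating the veterans with PTSD".

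The protocol has a separate controlled element under Aim 1: "we will administer a sham treatment and a TILS treatment in a randomized sequence during the first two weeks". The outcomes to be compared there include "the incremental changes of prefrontal activations and scores from three neutral memory tasks, which will be measured by fNIRS before and after the treatment". The SAP text available specifies a TILS-versus-sham model for one outcome only: "The mean CCO changes during the treatment period will be analyzed with repeated measures ANOVA". One part of the SAP was not available to this review, so statements about what the SAP does not say are limited to the text supplied.

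**The concern.** The question put is whether activity goes up. The answer given is that activity has stabilised. Six sessions that each do nothing are perfectly stable, and so are six that each lower activation by the same amount. The rule contains no comparison with zero, no comparison with sham and no direction, and it reaches its conclusion from a non-significant result.

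At stake is the deliverable of Aim 2. The rule can produce a number of sessions described as optimal for veterans with PTSD without itself giving any evidence that those sessions raised prefrontal activity. A null sham comparison at visits 3–4 would leave that number unchanged.

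**Working it through.** The documents give no sample size, SD, correlation or power for Aim 2, so there is no figure of the plan's to reproduce. Steps 1 and 4 need no assumed values.

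**1. What the F test can see.** With n veterans, k = 7 − i sessions and two sexes,

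F = [n Σ(ȳ_j − ȳ)² / (k − 1)] / [SS_error / ((n − 2)(k − 1))],

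where ȳ_j is the mean of session j, and each error residual is the observation minus the veteran's mean, minus the session mean within sex, plus the sex mean. Add c to every change. Each numerator term becomes (ȳ_j + c) − (ȳ + c), which is unchanged. Each residual gains c − c − c + c = 0. So F is the same for any c, positive or negative. Numerically, adding −0.5, +0.8 or +10 SD changed F by at most 4 × 10⁻¹⁵.

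**2. Flat response, one outcome, p < 0.05.** If all six true means are equal, the test at i = 1 is non-significant with probability 1 − 0.05 = 0.95, whatever their common value. Simulation (assumed: total SD 1, between-session correlation 0.5, sexes balanced, 4,000 runs; Monte Carlo standard error √(0.95 × 0.05/4000) = 0.003) agrees:

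| True change at every session | Session 1 named, N = 10 | N = 20 | N = 40 |
|---|---|---|---|
| 0 (inert) | 95.2% | 95.2% | 95.1% |
| −0.8 SD (harmful) | 95.1% | 95.5% | 94.9% |
| +0.8 SD (beneficial) | 95.6% | 94.6% | 94.9% |

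An inert device receives one of sessions 1–5 in about 99% of trials. With first-order autoregressive correlation of 0.5–0.8 and no sphericity correction, the 95% becomes 92–94%.

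**3. Do the other conditions help?** Activation and score in three tasks make 2 × 3 = 6 outcomes. The SAP's either/or wording leaves their combination open. The reading that makes session 1 hardest to name is that all six must be non-significant. If they are independent, that gives 0.95⁶ = 73.5%. At correlation 0.5 between outcomes it is about 79%, and at 0.8 about 85%. The overall range is about 73–86%, and 93–97% of inert devices still receive one of sessions 1–5.

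The effect-size condition works the wrong way, because it makes a significant difference harder to declare. Read as Cohen's f, f² = F × df₁/df₂. At N = 10 and i = 1, f > 0.8 therefore needs F(5, 40) > 0.64 × 40/5 = 5.12, p about 0.001. Session 1 is then named in 99.8–100% of trials in all three cases.

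**4. The last step.** At i = 6, k = 1 and the numerator degrees of freedom are 0. There is nothing to test, and no outcome is written for the case where none of steps 1–5 passes.

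**5. With a direction criterion added.** At the first i with p ≥ 0.05, also require the 95% confidence interval (t, N − 2 degrees of freedom) for the mean change over sessions i to 6 to lie above 0. One outcome, correlation 0.5, 6,000 runs:

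| True pattern | Number declared, N = 10 | N = 20 | N = 40 |
|---|---|---|---|
| Inert | 2.5% | 2.8% | 2.7% |
| −0.5 SD throughout | 0% | 0% | 0% |
| +0.5 SD throughout | 46% | 78% | 97% |
| +0.8 SD throughout | 81% | 98% | 99% |

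The amended rule separates cases that the written rule treats alike.

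**The case against.** The strongest reply is that Aim 1 already tests direction. A reader might infer from the dosage rule that the trial has no controlled evidence on whether TILS raises activation. The documents do not support that: the protocol plans a randomised TILS-versus-sham comparison of activation and memory-score changes at visits 3–4. This limits the point but does not answer it. The comparison covers one TILS session, says nothing on whether a rise persists over sessions i to 6, and is not a condition of the dosage rule.

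A reader might also infer that the endpoint is undefined, because stability could mean a repeated rise within each visit or a sustained level between visits. The SAP settles this by naming post-minus-pre changes. An analysis of the pre-treatment scans (Table 1: "Pre-treatment fNIRS scan TILS; bbNIRS measurement Post-treatment fNIRS scan") would be an optional alternative, not a correction.

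Two further replies stand. For a device with a constant benefit, naming session 1 fits the stated search for the least number, so the error concerns inert and harmful devices. The i = 6 gap is minor: with one outcome, an inert flat device gets that far in about 1% of trials.

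**Conclusion.** The rule is wrong as written, not merely short of detail. Its only test is unaffected by the overall mean change, so its output carries no information on up-regulation. That conclusion is algebraic and rests on no assumed input.

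The 95% follows from the 0.05 level, a flat response, one outcome and sphericity, and does not depend on N. The 73–86% also depends on the correlation between outcomes. All performance figures for the amended rule depend on the assumed N, SD and correlations.

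The finding concerns the Aim 2 rule. It does not extend to saying that the trial as a whole cannot test whether TILS acts.

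**What to change.** 1. Keep the specified post-minus-pre endpoint. At the first i that passes the stability test, also require the mean change over sessions i to 6 to have a 95% confidence interval above 0, on activation and memory measures named in advance, preferably one primary activation measure. Otherwise report 'up-regulation not shown'.
2. Run the iteration for i = 1 to 5 only, and add the outcome 'no stable number of sessions identified'.
3. Report the randomised visit 3–4 TILS-minus-sham contrast in activation and memory changes, allowing for visit order, beside any Aim 2 result. If it does not favour TILS, do not attribute a rise to TILS.
4. Report the number named with confidence intervals for the session differences, not as a proven optimum. A sustained-level analysis of the pre-treatment scans may be added as a sensitivity analysis.

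The change costs SAP wording and contrasts on data already planned, with no new visits. Its downsides, at assumed N = 10/20/40, are:

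- **The trial may name no number.** With one outcome, +0.5 SD is declared in about 44–46%, 76–78% and 97% at between-session correlation 0.5. At 0.8 the rates are about 32–33%, 64% and 91%; at 0.2 they are about 66–68%, 93–94% and 99%. If all six outcomes must meet the criterion, they fall to about 1–18%, 22–59% and 81–91%, and +0.8 SD at N = 10 is declared in about 29–63%. This is why one primary measure is preferable.
- **Carry-over is missed.** If the effect persists into later pre-treatment scans, so that the change is 0.8 SD once and then 0, a number is declared in only 4%, 3% and 2%.
- **Practice or time is not excluded**, because visits 5–9 have no concurrent sham. With an assumed drift of 0.05 SD per visit, an inert device passes in 10%, 18% and 34%; at 0.1 SD, in 29%, 59% and 87%. Item 3 addresses this only in part.
- **Non-significance remains weak evidence of stability.** With a true rise to 0.8 SD that levels off at session 4, the p-value rule names an earlier session in about 91%, 81% and 63%. Item 4 discloses this but does not cure it.
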